3.2 Exclusion Criteria

- 3.2.1 Hydroxychloroquine-specific rule-outs:
 - 3.2.1a. Receipt of HCQ within the past 6 months
 - 3.2.1b. History of allergic reactions attributed to compounds of similar chemical or biologic composition to hydroxychloroquine
 - 3.2.1c. Use of contraindicated medications, including but not limited to combination antiretroviral therapy and enzyme-inducing anti-epileptics (see **Appendix B**)
- 3.2.2 Macular degeneration or concurrent macular disease. Eligibility in the presence of other eye / visual impairments (cataracts, severe retinopathy, severe visual impairment at baseline, presence of only one functional eye) will be at the discretion of the treating physician based on eye exam by ophthalmologist.
- 3.2.3 Prior treatment with ADT including:
 - ADT for treatment of metastatic disease
 - ADT as adjuvant therapy prior to surgery/radiation within 1 year of enrollment
- 3.2.4 Previous history of radiation or surgery to a metastatic site
- 3.2.5 Previous treatment with any of the following:
 - Abiraterone -Enzalutamide -Apalutamide -antiretroviral therapy
 - chemotherapy -immunotherapy -radioisotopes
- 3.2.6 Serum testosterone less than 50 ng/ml
- 3.2.7 History of orchiectomy
- 3.2.8 History of pathologic fracture or spinal cord compression
- 3.2.9 Brain or CNS metastases
- 3.2.10 History of G-6-PD (glucose-6-phosphate dehydrogenase) deficiency
- 3.2.11 Uncontrolled intercurrent illness including but not limited to the following:
 - ongoing or active infection -symptomatic congestive heart failure
 - unstable angina pectoris -cardiac arrhythmia
- 3.2.12 Psychiatric illness and/or social situations that would limit compliance with study requirements.
- 3.2.13 Patients taking other investigational agents

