
 - Men ages 18 and older with recurrent prostate cancer following primary treatment of localized disease with either surgery or radiation - Recurrence defined as PSA ≥ 0.2 ng/dl following prostatectomy OR a PSA increase ≥ 2 above nadir following radiotherapy of primary tumor - ≤ 5 synchronous metastatic lesions on CT C/A/P and/or fluciclovine or prostate-specific membrane antigen scan - ECOG 0-2 	
 - Brain or CNS mets - Prior XRT/surgery to a metastatic site; orchectomy - Prior ADT for metastatic disease or as adjuvant therapy in past two years - Hx of fracture or spinal cord compression - Currently treated with abiraterone, enzalutamide, apalutamide, chemotherapy, immunotherapy or radioisotopes - Macular degeneration - Serum testosterone less than 50 ng/ml - Receipt of HCQ in the past 6 months

STUDY ENDPOINTS

Primary: 3-mos PAR-4 levels

Secondary:

Median Progression-Free Survival and 1-yr ADT-Free Survival up to 3 years
 HCQ Toxicity and Tolerability
 Quality of Life

Correlatives: PBMCs (days 0, 30, 60 of HCQ treatment), immune function and activation, systematic inflammation, and autophagy induction

TABLE OF CONTENTS	Pages
Title Page / Protocol History & Summary of Changes	1 / 3
SCHEMA	4
Table of Contents	5-6

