3. PATIENT SELECTION – ELIGIBILITY

3.1 Inclusion Criteria

- 3.1.1 Males age 18 and over
- 3.1.2 Histologically confirmed prostate cancer that has recurred following primary definitive treatment of localized prostate cancer (either surgery, radiotherapy or both)
 - PSA biochemical recurrence defined as either:
 - PSA \geq 0.2 ng/dL following radical prostatectomy
 - PSA increase \geq 2 ng/mL above PSA nadir value following radiotherapy of primary tumor
- 3.1.3 Five or fewer synchronous metastatic lesions (on imaging) with no evidence of residual local disease
- 3.1.4 ECOG performance status 0 – 2 (see **Appendix A**)
- 3.1.5 Approval by screening eye exam (disqualifying baseline conditions listed in 3.2.2, below)
- 3.1.6 Ability to provide informed consent

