4.2 Enrollment Guidelines

Patients who have received previous treatment for prostate cancer with the intent to cure who have biochemical recurrence will undergo metastatic evaluation with imaging at baseline including fluciclovine or prostate-specific membrane antigen (PSMA) PET scan (preferred), bone scan, PET/CT and/or CT of the chest, abdomen, and pelvis as needed to assess for metastatic disease.

Biochemical recurrence for patients who have previously undergone radical prostatectomy is defined as a PSA ≥ 0.2 ng/dl. Patients who have biochemical recurrence following radical prostatectomy should have received postoperative radiotherapy to the prostate bed if no evidence of metastatic disease.

For patients who have previously undergone primary treatment of their prostate cancer with radiotherapy, biochemical recurrence is defined as an increase of 2 or more ng/dl above the nadir. Patients who have undergone primary radiotherapy will have pelvic MRI to rule out local disease as part of the requisite baseline imaging. Suspicious lesions within prostate bed will be assessed by biopsy.

Patients with 1-3 metastatic lesions on metastatic evaluation will be further screened per inclusion and exclusion criteria as noted above, Section 3. Initial localization of metastases will be recorded (node vs bone vs visceral).

Eligible patients will be identified by the principal investigator and co-investigators of this study. Potentially eligible patients will be screened in the University of Kentucky Markey Cancer Center clinics by the investigators, study personnel, and the Principal Investigator (PI). Upon obtaining proper consent, patients will be enrolled into the study.

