11.3 Four Types of Disease Progression

1. **PSA or Biochemical Progression:** defined as a PSA increase of $\geq 25\%$ and ≥ 2 ng/mL if PSA was ≥ 2 ng/mL from baseline (OR a PSA increase of $\geq 25\%$ if PSA was < 2 ng/mL at study enrollment).
2. **Symptomatic Progression:** defined as increasing pain from baseline-detected metastatic lesion. Time to first symptomatic event will be calculated from study enrollment until the event of symptoms due to metastatic disease.
3. **Local Progression of baseline-detected lesions depend on site:**
 - 3a. ***soft-tissue metastatic lesion:*** local progression is defined as an increase of $\geq 20\%$ in the largest tumor dimension with a minimum absolute increase of 5 mm. All lesions are considered target lesions, irrespective of size, if they are suspicious on choline PET-CT. See Appendix H.1 for RECIST v1.1.
 - 3b. ***bone metastases:*** local progression is assessed using the MD Anderson Cancer Center-criteria²⁶⁻²⁷, and defined as a $\geq 25\%$ increase in size of a measurable lesion or a $\geq 25\%$ increase in the size of ill-defined lesions on CT considered to be progression. MDA bone-specific response criteria in Appendix H.2.
4. **Distant Progression:** appearance of new metastatic lesions

11.4 Definition of Disease Assessments to evaluate Progression-Free Survival and ADT-Free Survival

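### Units in the PSA and testosterone eligibility thresholds contradict each other or cannot be applied as written

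*Combined protocol and SAP*

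**What the plan says.** The eligibility thresholds appear in the schema (Figure 1), section 3 and section 4.2.

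- **PSA rise after primary radiotherapy.** Section 3.1.2 sets it at "2 ng/mL above PSA nadir value following radiotherapy of primary tumor". Section 4.2 says that "biochemical recurrence is defined as an increase of 2 or more ng/dl above the nadir". The schema gives a rise of 2 above nadir with no unit.
- **Testosterone.** Section 3.2.6 excludes men with "Serum testosterone less than 50 ng/ml", and the schema repeats the same figure and unit. The criterion stands with the prior-ADT exclusion (3.2.3) and "History of orchiectomy" (3.2.7). Section 5.1 lists total testosterone among the required screening tests but names no unit.
- **PSA after prostatectomy.** All three places use ng/dL: "0.2 ng/dL following radical prostatectomy" in 3.1.2, "radical prostatectomy is defined as a PSA ≥ 0.2 ng/dl" in 4.2, and "Recurrence defined as PSA ≥ 0.2 ng/dl following prostatectomy" in the schema.
- **PSA progression.** The definition in section 11.3 is in ng/mL ("ng/mL if PSA was" is part of it), and section 11.4.2 also uses ng/mL.

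The documents give no reference range or castrate cut-off for testosterone.

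**The concern.** These figures decide who may enter the trial. For the post-radiotherapy rise, two sections of one document give rules 100-fold apart, and a screener cannot follow both. For testosterone, the written unit puts the cut-off far above any level expected in an adult man. The rule would then exclude the men the trial wants to study. For the post-prostatectomy threshold, the unit differs from that of the radiotherapy rule listed directly below it, in a document that has demonstrably interchanged mL and dL for PSA elsewhere.

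What is at stake is a clear definition of the study population. If staff apply a sensible but unwritten reading, the eligibility record no longer matches the protocol. An auditor reading 3.2.6 literally would find nearly every enrolled man in breach of it.

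**Working it through.** The plan contains no calculation to reproduce on this point. The check is unit conversion, then a comparison of sections.

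**Conversion.** 1 dL = 100 mL, so ng/mL × 100 = ng/dL, and ng/dL ÷ 100 = ng/mL.

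| Threshold | Where | As written | In ng/mL |
|---|---|---|---|
| PSA rise after radiotherapy | 3.1.2 | 2 ng/mL | 2 |
| PSA rise after radiotherapy | 4.2 | 2 ng/dl | 2 ÷ 100 = 0.02 |
| PSA rise after radiotherapy | Schema | 2, no unit | undetermined |
| PSA after prostatectomy | Schema, 3.1.2, 4.2 | 0.2 ng/dL | 0.2 ÷ 100 = 0.002 |
| Testosterone exclusion | Schema, 3.2.6 | below 50 ng/ml | 50 (= 50 × 100 = 5,000 ng/dL) |

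**Post-radiotherapy rise.** The ratio of the two written rules is 2 ÷ 0.02 = 100. Any rise of at least 0.02 but less than 2 ng/mL satisfies 4.2 and fails 3.1.2. For example, a rise of 0.5 ng/mL is 50 ng/dL, which is above the 4.2 threshold of 2 ng/dl and below the 3.1.2 threshold of 2 ng/mL. This contradiction needs no outside source.

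**Testosterone.** The documents give no range, so one is assumed: normal adult male total testosterone of about 2.5 to 12 ng/mL (250 to 1,200 ng/dL).

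- Against the upper limit: 50 ÷ 12 = 4.2.
- Against the lower limit: 50 ÷ 2.5 = 20.
- With other assumed upper limits: 50 ÷ 10 = 5.0 and 50 ÷ 8 = 6.25.
- Stress test: even a tripled upper limit, 3 × 12 = 36 ng/mL, lies below 50.

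Across all these values, a man with normal testosterone falls below the cut-off and is excluded. The same digits in ng/dL would be 50 ÷ 100 = 0.5 ng/mL, 100-fold lower.

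**Post-prostatectomy threshold.** The three statements agree, so there is no direct contradiction. The doubt comes from the ng/mL unit in the adjacent 3.1.2 rule and in 11.3 and 11.4.2, together with the interchange shown for the radiotherapy rule. The same digits in ng/mL would be 0.2 ÷ 0.002 = 100 times higher.

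**Sample size.** Section 13.1.2 uses n = 18, proportions 0.20 and 0.50, and a two-sided 5% level. None of these depends on a PSA or testosterone unit. The one-sample normal approximation gives Φ[(0.30 − 1.96 × √(0.2 × 0.8/18)) ÷ √(0.5 × 0.5/18)] = 0.836, in line with the stated 84%.

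**The case against.** The strongest reply is that these are labelling slips that experienced staff would read correctly. The testosterone rule cannot be applied literally without halting enrolment, so sites would be expected to notice it. The history page records opening to accrual on 12/3/2019. It then lists an eligibility amendment covering only cataracts and the number of lesions, and later amendments that mention no difficulty with testosterone or PSA. That makes a practical workaround plausible, but it does not show which rule was applied, and the text still needs correcting.

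A second reply is that PSA is not the only gate. Section 3.1.3 also requires metastatic lesions on imaging with no residual local disease. A man with a PSA of 0.002 ng/mL, or a rise of 0.02 ng/mL, would still need image-detected metastases. This stands: the PSA units may change few enrolment decisions.

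A third reply is that the documents are consistent on testosterone, so calling the unit wrong relies on outside physiology and on a guess at intent. This is partly right. The range is an assumption, and the purpose of excluding castrate men is inferred from the neighbouring ADT and orchiectomy criteria. The conclusion is nevertheless insensitive to the range chosen.

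A reader might also infer that the post-prostatectomy threshold is proved wrong and that every PSA figure should simply be relabelled ng/mL. The documents do not support that. The threshold is the same in all three places, and PSA progression is a different construct from recurrence. The evidence justifies asking for confirmation only.

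**Conclusion.** The defect is real and should be corrected. The firmest part is the 100-fold contradiction between 3.1.2 and 4.2 on the post-radiotherapy rise, with no unit in the schema to settle it. The testosterone exclusion is unworkable as written: it is about 4 times the assumed upper limit of normal and 20 times the lower. The post-prostatectomy unit is doubtful but not contradicted.

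A reader might infer that the wrong men were enrolled, or that the whole cohort is ineligible. The documents contain no enrolment data and do not show this; it follows only if the testosterone rule is applied to the letter. The primary endpoint, power and sample size do not depend on these units. The finding therefore concerns an unclear study population and eligibility record. It does not invalidate the analysis.

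**What to change.** The sponsor should:

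1. Confirm the intended testosterone cut-off and each intended PSA threshold, figure and unit together. This review does not say which values are right.
2. Reconcile the schema and sections 3.1.2, 3.2.6 and 4.2 so that each analyte has one stated unit throughout, including the schema's radiotherapy rule, which has none. Check that the PSA unit chosen agrees with sections 11.3 and 11.4.2.
3. Check enrolled patients' screening PSA and testosterone against the reconciled rules, and document any who do not meet them.

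The cost is a minor protocol amendment and a review of screening results for a planned 20 patients. No analysis needs to change.

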3.3 Inclusion of Women, Minorities and Children

Prostate cancer does not occur in women nor in male children; as such, these groups are excluded from this study. No eligible male participants will be excluded from this study on the basis of race or ethnicity.

4. STUDY REGISTRATION PROCEDURES

4.1 Protocol Review and Monitoring Committee and Institutional Review Board Review

Before implementing this study, the protocol must be reviewed by the Markey Cancer Center's Protocol Review and Monitoring Committee. The protocol, the proposed informed consent form and other information to subjects must be reviewed by the University of Kentucky Institutional Review Board (IRB). A signed and dated UK IRB initial review approval memo must be maintained in the Markey Cancer Center Clinical Research Office (MCC CRO) regulatory binder. Any amendments to the protocol, other than administrative ones, must be reviewed and approved by the PRMC, study sponsor, and the UK IRB.

4.2 Enrollment Guidelines

Patients who have received previous treatment for prostate cancer with the intent to cure who have biochemical recurrence will undergo metastatic evaluation with imaging at baseline including fluciclovine or prostate-specific membrane antigen (PSMA) PET scan (preferred), bone scan, PET/CT and/or CT of the chest, abdomen, and pelvis as needed to assess for metastatic disease.

Biochemical recurrence for patients who have previously undergone radical prostatectomy is defined as a PSA ≥ 0.2 ng/dl. Patients who have biochemical recurrence following radical prostatectomy should have received postoperative radiotherapy to the prostate bed if no evidence of metastatic disease.

For patients who have previously undergone primary treatment of their prostate cancer with radiotherapy, biochemical recurrence is defined as an increase of 2 or more ng/dl above the nadir. Patients who have undergone primary radiotherapy will have pelvic MRI to rule out local disease as part of the requisite baseline imaging. Suspicious lesions within prostate bed will be assessed by biopsy.

Patients with 1-3 metastatic lesions on metastatic evaluation will be further screened per inclusion and exclusion criteria as noted above, Section 3. Initial localization of metastases will be recorded (node vs bone vs visceral).

Eligible patients will be identified by the principal investigator and co-investigators of this study. Potentially eligible patients will be screened in the University of Kentucky Markey Cancer Center clinics by the investigators, study personnel, and the Principal Investigator (PI). Upon obtaining proper consent, patients will be enrolled into the study.

4.3 Informed Consent

The goal of the informed consent process is to provide people with sufficient information so they can make informed choices about whether to begin or continue participation in clinical research. The process involves a dynamic and continuing exchange of information between the research team and the participant throughout the research experience. It includes discussion of the study's purpose, research procedures, risks and potential benefits, and the voluntary nature of participation.

The informed consent document provides a summary of the clinical study and the individual's rights as a research participant. The document acts as a starting point for the necessary exchange of information between the investigator and potential research participant. Also, research participants and their families may use the consent document as an information resource and reference throughout participation in the trial. The informed consent document is often considered the foundation of the informed consent process; it does not, however, represent the entirety of the process. Nor is the informed consent document a risk-management tool for the investigator and/or institution.

The investigator must explain to each subject the nature of the study, its purpose, the procedures involved, the expected duration, the potential risks and benefits involved and any discomfort it may entail. Each subject must be informed that participation in the study is voluntary and that he may withdraw from the study at any time and that withdrawal of consent will not affect his subsequent medical treatment or relationship with the treating physician.

This informed consent should be given by means of a standard written statement, written in non-technical language. The subject should read and consider the statement before signing and dating it, and should be given a copy of the signed document. No patient can enter the study before his informed consent has been obtained. The informed consent form is considered to be part of the protocol, and must be submitted by the investigator with the protocol at the time of IRB review.

4.4 Compliance with Laws and Regulations

The study will be conducted in accordance with U.S. Food and Drug Administration (FDA) and International Conference on Harmonization (ICH) Guidelines for Good Clinical Practice (GCP), the Declaration of Helsinki, any applicable local health authority, and Institutional Review Board (IRB) requirements. The study PI or designee will be responsible for obtaining continuing and not less than annual IRB re-approval throughout the duration of the study. Copies of the Investigator's annual report to the IRB and copies of the IRB continuance of approval must be maintained by the MCC CRO. The study PI or designee is also responsible for notifying the Data and Safety Monitoring Committee of the MCC and the UK IRB of any significant adverse events that are serious and/or unexpected, as per SOP's of those entities. The MCC DSMC will review all adverse events of this IIT as per its SOP.

5. TREATMENT PLAN

5.1 Enrollment and Screening Process

Prior to any study-required tests, subjects must first provide written informed consent to participate in this study.

All lab tests, ophthalmologic exam and radiographic studies should be completed within eight weeks prior to initiation of HCQ treatment.

Complete history, physical examination, and evaluation of performance status will also be performed during this 8-week timeframe.

Required lab work will include:

complete blood count (CBC); serum chemistry tests to include alkaline phosphatase, glucose, creatinine, electrolytes, AST (SGOT), total testosterone, and total bilirubin.

5.2 Metastatic site-directed treatment and hydroxychloroquine administration

Modality of site-directed treatment of oligometastatic lesions will be decided by multidisciplinary team consisting of urologic surgery, radiation oncology, and medical oncology in consultation with the patient.

5.3 HCQ Administration

Hydroxychloroquine will be administered daily on an outpatient basis beginning 2 weeks before metastasectomy or initiation of radiation treatment to metastatic lesions. HCQ administration will be held the day of surgery for those patients undergoing surgical resection of their metastatic site(s) and will resume on post-operative day 1, and the missed dose will not be made up. Hydroxychloroquine will be administered orally at a total daily dose of 400 mg (200 mg BID) for 90-days. Tablets of HCQ are available in 200 mg strength.

Instructions on taking HCQ (patient version) are located in **Appendix C**.

To minimize nausea, HCQ is recommended to be administered in divided doses (one 200-mg tablet twice per day). The divided doses should be taken with meals, once in the morning and once at night. Should a subject have emesis and regurgitate the HCQ within 30 minutes of taking it, the dose may be repeated once, but if vomiting occurs longer than 30 minutes after ingestion, the dose should not be repeated.

Study participants will be required to keep a medication diary and to present the completed diary at the end of the treatment (**Appendix D**). Additionally, at the PI's discretion, study staff will call the participants periodically on an as-needed basis to monitor ongoing completion of the pill diaries while patient is on-study, e.g., if a patient misses a clinic visit.

Appropriate dose modifications are described in Section 6.

Adverse events and potential risks are described in Section 7.

5.4 General Concomitant Medication and Supportive Care Guidelines

Because there is a potential for interaction of hydroxychloroquine with other concomitantly administered drugs through the cytochrome P450 system, the case report form must capture the concurrent use of all other drugs, over-the-counter medications, or alternative therapies. The PI should be alerted if the patient is taking any agent known to affect or with the potential to affect selected CYP450 isoenzymes. **Appendix B** presents guidelines for identifying medications/substances that could potentially interact with hydroxychloroquine. While not strictly prohibited, these medications should be avoided if at all possible. Hydroxychloroquine should also be used with caution in patients taking medicines that may cause adverse ocular or skin reactions.

5.5 Duration of Therapy

In the absence of treatment delays due to adverse event(s), hydroxychloroquine treatment will continue for 3 months or until one of the following criteria applies:

- Disease Progression, assessed by standard of care and defined as either:
 - PSA progression (an increase in PSA > 25% above baseline at study entry), or
 - Symptomatic progression (increasing pain from metastatic lesion), or
 - Progression of baseline-detected lesions (soft-tissue lesions as assessed by RECIST and bone lesions as assessed by the MDA criteria (respectively, Appendix H.1 and Appendix H.2)).
Additionally, CT C/A/P and/or fluciclovine or PSMA PET scans may be performed at the time of either Symptomatic or PSA Progression at discretion of the treating physician.
 - Appearance of new metastatic lesions
- Intercurrent illness that prevents further administration of treatment
- Unacceptable adverse event(s)
- Patient decides to withdraw from the study
- General or specific changes in the patient's condition that render the patient unacceptable for further treatment in the judgment of the investigator

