11.4.2 Progression-Free Survival (time to clinical progression)

Four types of progression are defined in 11.3. Progression is calculated from time of study enrollment until progression (per the 4 specified definitions) or death. Events for PFS are:

1. PSA or biochemical progression: defined as a PSA increase of $\geq 25\%$ and ≥ 2 ng/mL (if PSA was ≥ 2 ng/mL from baseline)
2. Symptomatic progression: increasing pain from metastatic lesion
3. Local progression of baseline-detected lesions: each metastasis is a target lesion independently assessed as:
 - soft-tissue lesions assessed per RECIST v1.1 (Appendix H.1)
 - bone lesions assessed per MDA bone-specific response criteria (Appendix H.2)
4. Distant progression: appearance of new metastatic lesions.

If an event is identified, then the time to the event will be recorded as the first instance where any of the above four situations occur.

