APPENDIX H 1-2 – Response Criteria for Disease Progression

- **H.1 RECIST v1.1 for soft-tissue metastatic lesions**
- **H.2 MDA Criteria for bone-specific response criteria**

H.1 Response Evaluation Criteria in Solid Tumors (RECIST 1.1)* to be used for soft-tissue metastatic lesions	
Response category	Criteria
Complete response	Disappearance of all target lesions
	Reduction in short axis of target lymph nodes to < 10 mm
Partial response	Decrease in target lesion diameter sum $\geq 30\%†$
Progressive disease	Increase in target lesion diameter sum $\geq 20\%‡$
	≥ 5 mm increase in target lesion diameter sum
	New, malignant FDG uptake in the absence of other indications of progressive disease or an anatomically stable lesion, and confirmed on contemporaneous or follow-up CT
	Unequivocal progression of nontarget lesions
Stable disease	Does not meet other criteria‡

*Measurements are based on the sum of the unidimensional measurement of the greatest diameter of a maximum 5 lesions.

†Reference standard: baseline sum. ‡Reference standard: smallest recorded sum. Table modified from Eisenhauer et al.

H.2 MD Anderson Cancer Center-Criteria for bone response criteria for bone metastases *	
Response category	Criteria
Complete response	Complete sclerotic fill-in of lytic lesions on XR or CT
	Normalization of bone density on XR or CT
	Normalization of signal intensity on MRI
	Normalization of tracer uptake on SS
Partial response	Development of a sclerotic rim or partial sclerotic fill-in of lytic lesions on XR or CT.
	Osteoblastic flare - Interval visualization of lesions with sclerotic rims or new sclerotic lesions in the setting of other signs of PR and absence of progressive bony disease
	$\geq 50\%$ decrease in measurable lesions on XR, CT, or MRI
	$\geq 50\%$ subjective decrease in the size of ill-defined lesions on XR, CT, or MRI
	$\geq 50\%$ subjective decrease in tracer uptake on SS
Progressive disease	$\geq 25\%$ increase in size of measurable lesions on XR, CT, or MRI
	$\geq 25\%$ subjective increase in the size of ill-defined lesions on XR, CT, or MRI
	$\geq 25\%$ subjective increase in tracer uptake on SS
	New bone metastases
Stable disease	No change
	$< 25\%$ increase or $< 50\%$ decrease in size of measurable lesions
	$< 25\%$ subjective increase or $< 50\%$ subjective decrease in size of ill-defined lesions
	No new bone metastases

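### The PSA event in PFS is referenced to the pre-treatment entry value and never to the post-treatment nadir, so PFS can only come out equal to or later than under a nadir rule, by an amount the documents do not fix

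*Combined protocol and SAP*

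**What the plan says.** PFS is a secondary endpoint, estimated by Kaplan-Meier (13.3.2). Section 11.4.2 sets its clock and its event: "Progression is calculated from time of study enrollment until progression (per the 4 specified definitions) or death", and "the time to the event will be recorded as the first instance where any of the above four situations occur". The four types are PSA, symptomatic, local and distant progression.

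The PSA event in 11.4.2 requires a rise of at least 25% and at least 2 ng/mL for men at or above 2 ng/mL. The only reference named there and in the matching branch of 11.3 is baseline ("2 ng/mL from baseline"). For men below 2 ng/mL, 11.3 asks for a 25% rise, with the branch set by the value in "ng/mL at study enrollment". Section 11.4.2 has no rule for those men.

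Section 5.5, the HCQ stopping rule, names the reference outright: "PSA progression (an increase in PSA > 25% above baseline at study entry".

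Under 5.3, HCQ starts two weeks before metastasectomy or radiation, so an entry PSA is a pre-treatment value. A PSA nadir is used only for eligibility after primary radiotherapy ("2 ng/mL above PSA nadir value following radiotherapy of primary tumor", 3.1.2; likewise the schema and 4.2). For soft-tissue lesions, progression in Appendix H.1 carries the note "Reference standard: smallest recorded sum".

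**The concern.** Every man in this trial has his metastases resected or irradiated soon after the baseline PSA. Where that works, PSA falls below entry. If it later climbs, the plan records no PSA event until the whole fall has been regained and a further 25% and 2 ng/mL added. The deeper the response, the longer the wait.

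The plan is also not uniform. A soft-tissue lesion that shrinks and regrows is judged from its smallest size, while a PSA that falls and rises is judged from its starting value.

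At stake are median PFS, the PFS rates at fixed times, and the exploratory Cox models relating PFS to PAR-4 and PSA. With no control arm there is no comparison in which a delay could cancel. PSA is the only progression marker with fixed on-study draws. Imaging follows clinical indicators and the treating physician's discretion (Study Calendar, note 6c). The last scheduled PSA is one year after HCQ stops, about month 15.

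**Working it through.** The plan states no figure for PFS or PSA progression, so there is none to reproduce. Its 84% power concerns the PAR-4 endpoint and does not enter here.

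**Rule.** For a man entering at 2 ng/mL or more, with reference value r, the PSA event level is T(r) = max(1.25 r, r + 2). The two parts cross where 0.25 r = 2, that is r = 8. Below 8 the 2 ng/mL part decides; above 8 the 25% part does.

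**Levels under the entry reference.** Entry 2 gives 4.0; 5 gives 7.0; 8 gives 10.0; 10 gives 12.5; 20 gives 25.0 ng/mL.

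**Delay against the same rule taken from the nadir.** Let B be the entry PSA and N the nadir. The extra wait is log2[T(B)/T(N)] doublings. Multiplying by the doubling time gives months, assuming exponential regrowth. The documents give neither depth of fall nor doubling time; both are assumed.

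| B | Fall | N | T(B) | T(N) | Doublings | Months at 6-month doubling |
|---|---|---|---|---|---|---|
| 5 | 50% | 2.5 | 7.0 | 4.5 | 0.64 | 3.8 |
| 5 | 80% | 1.0 | 7.0 | 3.0 | 1.22 | 7.3 |
| 5 | 90% | 0.5 | 7.0 | 2.5 | 1.49 | 8.9 |
| 10 | 50% | 5.0 | 12.5 | 7.0 | 0.84 | 5.0 |
| 10 | 80% | 2.0 | 12.5 | 4.0 | 1.64 | 9.9 |
| 10 | 90% | 1.0 | 12.5 | 3.0 | 2.06 | 12.4 |

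For entry 2 to 20 and a nadir of 10% to 50% of entry, the delay runs from 0.42 to 2.64 doublings. That is about 1.2 to 7.9 months at a 3-month doubling time, 2.5 to 15.9 at 6 months, and 5.0 to 31.7 at 12 months. With no fall it is zero.

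**Direction for PFS.** The lowest PSA since entry, entry included, is never above entry. T increases with r, so the nadir-referenced PSA event is never later than the entry-referenced one. PFS is the earliest of several events, so bringing one component forward leaves it unchanged or shortens it.

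**Size for PFS.** Assumed: entry PSA median 5, restricted to 2 or more; nadir at month 3; fall uniform from 30% to 90%; doubling time median 6 months; several spreads tried.

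- PSA event alone: median about 14.0 to 14.2 months (entry reference) against 8.1 to 9.2 (nadir). About 54% to 56% against 81% to 88% reach it by month 15.
- Adding an independent exponential non-PSA event with median 6, 9, 12 or 18 months: the gap in median PFS becomes about 0.8 to 1.0, 1.7 to 2.2, 2.3 to 2.9, or 3.1 to 3.8 months. Other assumed spreads move these by a few tenths of a month.

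**The case against.** A reader might infer that a relapsing responder stays progression-free until he passes his pre-treatment PSA, and that PFS is overstated by some five months. The documents do not support that. Under 11.4.2 he is free of PSA progression only; pain, local or distant progression, or death would still end his PFS. Note 6c lets a rising PSA prompt imaging without any threshold over baseline. The five-month gap comes from a calculation with every other event switched off.

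It is also fair to say that the explicit entry reference stands in the HCQ stopping rule, not in the PFS definition. In 11.3 and 11.4.2 the mention of baseline is attached to the 2 ng/mL condition, so entry is the natural reading of the reference but not a stated one.

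Baseline is a defined and reproducible choice, and a nadir is not thereby the truth. The parallel with 3.1.2 is weak: that nadir follows primary radiotherapy and serves eligibility, and men after prostatectomy have a fixed cut-off.

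Finally, accrual opened in December 2019 and the last dated amendment is from June 2023. Replacing the main definition now, in a single-arm trial, could look data-driven. PFS here is descriptive, in 20 men, with no benchmark.

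All of this stands and limits the point. It does not remove the one-directional delay, and the loose wording is itself a reason to state the reference.

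**Conclusion.** The point holds in a limited form. The only PSA reference named for PFS is a pre-treatment value, and no on-study PSA rule uses the nadir. For men entering at 2 ng/mL or more who respond, the PSA event is delayed by 0.4 to 2.6 doublings under the falls considered. PFS is therefore equal to or later than under a nadir rule, never earlier.

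The documents do not fix the size of the effect on PFS. It lies between zero, when another event comes first, and the full PSA delay. Roughly 1 to 4 months in the median is a plausible range, resting on assumed falls, doubling times and competing-event rates. The share of men at or above 2 ng/mL is also unknown, since eligibility after prostatectomy starts well below that.

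The primary endpoint, sample size and power are untouched. Severity: minor to moderate.

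**What to change.** For the PFS endpoint only:

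- In 11.4.2(1), state the PSA reference value explicitly. For men entering at 2 ng/mL or more, keep the rise of at least 25% and at least 2 ng/mL, and measure it from the lowest PSA recorded since entry, with the entry value included. Because 11.4.2 points back to 11.3, say that this derivation applies to PFS alone.
- Report PFS under both the nadir and the entry-value reference, specified before the PFS data are analysed.
- If the sponsor prefers not to change the main definition this late, keep the entry-value PFS and add the nadir-referenced PFS as a prespecified sensitivity analysis.
- Reconcile 11.3 and 11.4.2 for men entering below 2 ng/mL, who have a PSA rule in the first and none in the second.

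Confining the edit to 11.4.2 matters, because 11.4.1 lets ADT be considered at PSA progression and a change in 11.3 would move that point. No change is proposed to 11.4.1 or to the HCQ stopping rule in 5.5.

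The cost is a few lines of wording and one derived variable, the running minimum PSA, from values already collected. The downside is a somewhat shorter reported PFS.
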